Hence, the main purpose of this study is to use TMS treatment to maintain patients that have responded or remitted from their depressive symptoms from the use of clinical TMS treatment, while off their antidepressant medication. A secondary objective is to see how the safety and effectiveness of this newer treatment protocol (theta-burst) is compared to prior treatment protocols in a maintenance regime, by comparing the theta-burst to traditional 10hz TMS treatment protocols. An additional tertiary purpose is to see if maintenance therapy treatment performed by a certified TMS technician can be performed without the need of TMS Attending supervision. Given the relative safety of TMS, that TMS technicians are CPR certified, and highly experienced in understanding the safety of TMS, this particular objective would help to show the feasibility and possible economic benefit to patient and provider of not needing Attending supervision for TMS maintenance treatment.

II. Drugs/Biologics/Devices

The device used in this study is a Magventure/MagVita Transcranial Magnetic Stimulation device. It is a FDA approved for treating Major Depressive Disorder in an acute treatment protocol. The normal acute clinical treatment protocol consists of 36 treatments given over 6 weeks with a 3 week taper (totaling 9 weeks). This study will be looking at a maintenance protocol and treating monthly, so there will be much less treatments comparatively. There is no IDE required for this study since it is a FDA approved device and we will use FDA cleared treatment protocols. More specific inclusion criteria are listed in the inclusion/exclusion section of the protocol.

TMS is an electromagnet that uses a small precise, but powerful magnetic pulse delivered to the head corresponding to an area over the brain thought to have some role in the depressive symptoms associated with MDD. This study will use the exact same protocols used in the acute treatment setting, except that treatments will be given monthly not daily (see methods section for reference).

There are currently 3 FDA cleared treatment protocols for acute clinical treatment associated with this device. They consist of a 37 minute treatment, a 20min treatment, and a

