 - o Any drug or alcohol use deemed by the study doctor as unsafe for TMS treatment
- Subjects unwilling to sign consent or follow study procedures
- Subjects with known extended travel plans which may affect study procedures and scheduled TMS treatment

VI. Number of Subjects

For this study we are looking to enroll 120 subjects broken down between 2 different treatment arms in the following way:

The number of subjects we expect to enroll is based on our current UMHC Neuromodulation clinic patient flow. The average patient clinic flow is 100 per year and using these numbers the study should be able to complete within 1-2 years. We expect that at least 20% of our expected enrolled may drop out of study for varies reasons (moved, loss of interest, unexpected reasons) hence the total expected completed being 100. 60 subjects in each arm will allow for a balanced study.

VII. Study Procedures/ Design/Treatment Plan

This is an open-label non-blinded study, for patients that have already completed an acute TMS course of therapy and have responded or remitted from their depressive symptoms according to their routine care clinical assessments (PHQ-9, or QIDS). There is no sham treatment in this study, but we will be using a study arm that does not receive TMS treatment in order to compare to an active TMS study arm.

All subjects will complete 3 non-treatment visits (consent, baseline, end of study visit) and if a subject is in the treatment arm and additional 60 visits (over the course of year). Additionally, a subject that is in the treatment arm will completed a PHQ-9, and IDS at baseline visit, and the beginning and end of each monthly treatment block. If a subject is in the non-treatment arm they will complete 15 total visits consisting of a consent, baseline, 12 assessment visits (for PHQ-9 & IDS testing) and an end treatment visit. For these individuals, a PHQ-9 and IDS will be completed at the baseline visit and at each monthly assessment visit.

[figure not shown]

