Study procedure plan is below:

Study visit completion for TMS active arms form is below, subjects that are in non-active arm will not have the TMS treatment visits, but will do the monthly assessment visits:

Visit	Consent	Hipaa	Inclusion/Exclusion	TASS	PHQ-9*	QIDS*	AE **
Consent	x	x					
Baseline			x	x	x	x	
Trt 1-5 (1 Month)					x	x	
Trt 6-10 (2 Month)					x	x	
Trt 11-15 (3 Month)					x	x	
Trt 16-20 (4 Month)					x	x	
Trt 21-25 (5 Month)					x	x	
Trt 26-30 (6 Month)					x	x	
Trt 31-35 (7 Month)					x	x	
Trt 36-40 (8 Month)					x	x	
Trt 41-45 (9 Month)					x	x	
Trt 46-50 (10 Month)					x	x	
Trt 51-55 (11 Month)					x	x	
Trt 56-60 (12 Month)					x	x	

* Completed before and after each monthly TMS treatment block

** Adverse Event form to be filled out as needed

VIII. Potential Risks/Adverse Events

The machine and treatment protocols are the same used in the clinical setting, therefore the risks are the same. The most common side effect/ risk is headache, superficial pain under treatment site, dental pain, eye pain, or facial muscle twitching. These seem to well tolerated, and can occur during or after treatment. These can be treated with over-the-counter pain medication (Tylenol, Ibuprophen).

Another rare but serious risk is seizure. Seizures are very rare and are thought to occur about 1 in 30,000 treatments. Subjects will have already gone through safety screens in order to get TMS treatment clinically, but nevertheless, another Transcranial Adult Safety Screen (TASS) will be done prior to starting treatment phase of study. Study staff are trained in seizure occurrence during TMS and are also CPR certified.

The study doctor will determine if patient participation should start or continue from these or any other subject problems that may occur, such as failure of TASS question throughout the study.

If an adverse event, UP, or deviation occur study staff will fill out a study adverse event form, the AE event log, and will notify the MU IRB if required within 5 days of awareness of the event.

IX. Anticipated Benefits

It is not known whether TMS used in a monthly maintenance protocol will be beneficial in helping to extend out the subject's acute response or remission, but it may be a possible benefit. Additionally, this study will help add to the work of clinical and scientific community in this area of interest. This data may also help future patients that have MDD and are trying to maintain their response.

X. Compensation

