No compensation will be given for this study.

XI. Costs

There are no costs associated with this study either for the research or to participants. The TMS machine is already part of the Neuromodulation Clinic.

XII. Data Safety Monitoring Plan

No DSMB is required for this study. All adverse events will be reported on the AE study report form, the AE log, and local IRB protocol will dictate what needs to be submitted to MU IRB. Because this is an internal study (no other sites), AEs and UP will immediately be known to study doctor. He will determine if AEs are in the normal range

for TMS treatment, comparing to clinical experience and TMS safety data. If they are found not to be, the he may pause the study to review protocols and procedures.

All study data will be captured on paper then transferred over to an electronic database on a secured approved UM computer. All data will be coded so no patient data will be identifiable. Study Consents and HIPAA that are signed will be stored in locked cabinet behind a locked door. The key linking subject consent and subject codes will not be stored in same place as consents and coded data. All coded data on paper will be placed in subject binder and stored in locked cabinet behind locked door. All study data will be stored for length of time in accordance with UM IRB research data rules.

XIII. Multiple Sites

1. NA

XIV. References/Appendices

- 1 O'Reardon, J. P., Solvason, H. B., Janicak, P. G., Sampson, S., Isenberg, K. E., Nahas, Z., ... & Demitrack, M. A. (2007). Efficacy and safety of transcranial magnetic stimulation in the acute treatment of major depression: a multisite randomized controlled trial. *Biological psychiatry*, 62(11), 1208-1216.
- 2 Carpenter, L. L., Janicak, P. G., Aaronson, S. T., Boyadjis, T., Brock, D. G., Cook, I. A., ... & Demitrack, M. A. (2012). Transcranial magnetic stimulation (TMS) for major depression: a multisite, naturalistic, observational study of acute treatment outcomes in clinical practice. *Depression and anxiety*, 29(7), 587-596.
- 3 Janicak, P. G., Nahas, Z., Lisanby, S. H., Solvason, H. B., Sampson, S. M., McDonald, W. M., ... & O'Reardon, J. P. (2010). Durability of clinical benefit with transcranial magnetic stimulation (TMS) in the treatment of pharmacoresistant major depression: assessment of relapse during a 6-month, multisite, open-label study. *Brain stimulation*, 3(4), 187-199.

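### No visit schedules an enquiry about adverse events, so the secondary safety comparison of theta-burst with 10 Hz rests on spontaneous, open-label reports

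*Protocol*

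**What the plan says.** Section I (Research Objectives/Background) sets the objective: "A secondary objective is to see how the safety and effectiveness of this newer treatment protocol (theta-burst) is compared to prior treatment protocols". The comparator is the traditional 10 Hz protocol, and the setting is maintenance treatment.

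The visit schedule in Section VII has a column for adverse events. It carries no mark at consent, at baseline or at any of the 12 monthly blocks. Its footnote reads "Adverse Event form to be filled out as needed". In the same table the two depression scales are marked at baseline and at all 12 blocks, and a second footnote has them completed before and after each block.

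Two other places govern recording. Section VIII: "If an adverse event, UP, or deviation occur study staff will fill out a study adverse event form, the AE event log". Section XII: "All adverse events will be reported on the AE study report form, the AE log". Section XII also has the study doctor judge whether events fall in the usual range for TMS, against clinical experience and published safety data, with power to pause the study.

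The only scheduled safety instrument is the TASS, a pre-treatment screen marked at baseline. The no-TMS arm's monthly visits are described solely as occasions for the depression scales.

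**The concern.** Recording an event and finding out about it are separate steps. The protocol fixes the first and leaves the second to chance. The effects listed in Section VIII are headache, pain at the stimulation site, in the teeth or in the eyes, and facial twitching. Apart from twitching, these are known only if the subject mentions them or is asked. Section VIII adds that they may arise after a session as well as during it. One that follows the last session of a block occurs when no staff are present, and nothing prompts a question at the next block.

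Two consequences follow for the secondary objective. First, a visit with no form may mean no event or an event not mentioned, and no analysis can separate the two afterwards. Second, the study is open-label, so expectations about the newer or the older protocol can affect what is volunteered and what is noticed. The study doctor's review is exposed as well: an undercount set against outside data looks reassuring, to the extent that those data came from more active questioning.

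**Working it through.** **Is a blank cell meaningful?** The table has 14 rows: consent, baseline and 12 blocks. The depression-scale columns are marked in 13 of them, the adverse-event column in none. In a table that marks what is due at each visit, a blank means not scheduled, and the footnote confirms that the form is event-driven.

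**Visit counts.** The stated counts reproduce. Active arm: 12 blocks × 5 = 60 treatment visits ("if a subject is in the treatment arm and additional 60 visits (over the course of year"). No-TMS arm: 1 consent + 1 baseline + 12 assessments + 1 end visit = 15 ("If a subject is in the non-treatment arm they will complete 15 total visits").

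**Can a rate be formed?** Yes. Subjects and treatments are countable. The ceiling is 60 subjects × 60 treatments = 3,600, before dropout and removal for deterioration. The numerator is the log of events that came to light. What results is a rate of reported events, not incidence.

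**Could the serious event carry the comparison instead?** Section VIII puts seizure at about 1 in 30,000 treatments.
- Expected seizures: 3,600 / 30,000 = 0.12.
- Chance of at least one: 1 − (1 − 1/30,000)^3600 = 0.11.
- With none seen, the one-sided 95% upper limit is 1 − 0.05^(1/3600) = 0.00083, about 1 in 1,200 treatments.

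A seizure would hardly be missed under any schedule, but there will be too few to compare protocols. The comparison therefore depends on the mild events.

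**What does incomplete but equal capture cost?** The documents give no event rates, no capture rates and no split of the active arm between protocols in the text shown. Assumptions: true per-subject risks of 40% and 20%; two-sided 5% test; 30 per group (an even split of 60), with 60 per group as a generous bound; capture proportion c the same in both groups.

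Observed risks are p1 = 0.40c and p2 = 0.20c. With p̄ their mean, SE0 = √(2p̄(1−p̄)/n) and SE1 = √((p1(1−p1)+p2(1−p2))/n), so power = Φ((p1 − p2 − 1.96·SE0)/SE1).

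| Capture c | Observed risks | Power, 30 per group | Power, 60 per group |
|---|---|---|---|
| 100% | 40% v 20% | 0.39 | 0.67 |
| 75% | 30% v 15% | 0.28 | 0.50 |
| 50% | 20% v 10% | 0.19 | 0.33 |

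Worked case, c = 50%, n = 30: p̄ = 0.15, SE0 = 0.0922, SE1 = 0.0913; (0.10 − 0.1807)/0.0913 = −0.884; Φ = 0.19.

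Equal under-capture leaves the ratio of risks at 2 but halves the difference and roughly halves the power. Unequal capture would also distort the ratio. Nothing in the protocol indicates its size or direction, so no figure is put on it.

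**The case against.** The strongest reply is that Sections VIII and XII already make recording compulsory. Read with them, the footnote means that a form is completed whenever there is an event, and a blank column is just how event-driven recording looks in a schedule. Treated subjects are seen five times per block, so staff have many chances to hear of a complaint, and some effects occur while staff are present. Section VIII mentions failing a TASS question during the study, which suggests some continuing screening. The adverse-event form and any visit worksheet are not shown and may contain prompts. Spontaneous reporting is a recognised, if less sensitive, method in an open-label phase IV study.

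Much of this stands, and it rules out several stronger readings:

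- A reader might infer that toxicity cannot be compared or given a rate. The documents do not support that, because known events must be logged and the denominators are available.
- A reader might infer that the technician decides whether an event merits a form. The text gives no such discretion.
- A reader might treat the tertiary objective as a second safety question. It asks whether "maintenance therapy treatment performed by a certified TMS technician can be performed without the need of TMS Attending supervision", and its stated purpose is that "this particular objective would help to show the feasibility and possible economic benefit to patient and provider". Relative safety is its premise, not its named outcome.
- A reader might lean on the contact gap between arms (60 treatment visits against 12 assessments, a ratio of 5). The stated safety comparison is between two TMS protocols, for which the text gives one treatment-visit schedule. For the no-TMS arm, Section II names durability of response as the comparison.
- A reader might expect a spurious difference of a particular size between protocols. That requires assumed unequal capture, for which the documents offer no basis.

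What the reply does not meet is the missing enquiry. A duty to record does not create a duty to ask, the TASS is a screen and not a side-effect checklist, and a statistical analysis plan cannot recover events that were never elicited.

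**Conclusion.** The point holds as a cheap improvement to data collection, not as an error that invalidates the study. As written, the secondary safety comparison will use rates of spontaneously reported events. Those rates are likely to understate incidence and reduce power, and they may be unevenly captured because the study is open-label. On the assumed 40% and 20% risks with 30 per protocol, halving capture takes power from 0.39 to 0.19. Even full capture leaves power low on those figures, so events should not be lost needlessly.

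The conclusion rests on the protocol alone. It would weaken if the unseen form or worksheet already requires a standard question at each visit; in that case the schedule should say so. The risks, capture proportions and even split are illustrations, not figures from the documents.

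**What to change.** Mark the adverse-event column at the existing treatment visits. The minimum is the start and end of each monthly block, when the depression scales are already completed: 2 × 12 = 24 enquiries per treated subject. Asking at every treatment visit gives 60.

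Use one short form, identical for theta-burst and 10 Hz: a yes/no line for each effect named in Section VIII, one open question, and an explicit entry for none, so that absence of an event is recorded rather than presumed. Reword the footnote so that the full adverse-event form follows any positive answer, and keep the existing rule for events that come to light between visits.

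If adverse events are also to be compared with the no-TMS arm, ask the same item at its 12 monthly assessment visits with the same recall period, and base that comparison on the monthly item alone.

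The cost is an edit to the schedule, a one-page form, a minute or two at visits already planned, and more minor events on the log. No treatment or visit changes.

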If a potential subject is interested in learning more about the study a copy of the consent will be given or sent to them in the mail for them to review, and a consent appointment will be setup to meet with the study staff.

IV. Consent Process

When a potential subject is identified and after a copy of the consent is given to the potential subject for review, a consent appointment will be setup. At the appointment an approved study team member will go over the privacy practices, HIPAA, and consent thoroughly, allowing the potential subject to ask questions and stressing that the signing of the consent is not a contract only a process, and that they can discontinue the study at

any time for any reason. Then if the subject is interested in starting the study the approved team member will have the subject sign and date the HIPAA and consent. Then a copy of each signed document will be given to the subject. A baseline visit will then be setup, or if time allows a baseline visit commence immediately following the signing of consent.

V. Inclusion/Exclusion Criteria

Inclusion Criteria:

[figure not shown]
- Must have recently (within 4 weeks) completed an acute TMS course (full 36 treatments) at the UMHC Neuromodulation clinic
- Must have clinically responded to the acute TMS treatment course ($\geq 50\%$ improvement according to the clinical depressive scale used - usually the PHQ-9)
- Must be able sign consent
- Must have a current address and phone number
- Must have current mental health care provider, either psychiatrist or general practitioner who they see for mental health symptom management
- Must be able to taper off antidepressant medication within 2 months of signing consent of study (treatment group only)

Exclusion Criteria:

- Subject that has not completed a full acute treatment course, including taper
- Subjects that have changed anything that may not make them safe for TMS, which are (all changes will be reviewed by study MD, and will not necessarily be excluded possibly depending on severity):
 - o Any new metal near head
 - o Any new medical devices that cannot be removed
 - o Any new pregnancies (verbally confirmed)
 - o Seizures that occurred post-acute TMS treatment
 - o Any uncontrolled cardiovascular disease
 - o Any new head trauma
 - o Any new illness causing injury to brain
 - o Any new medications which cannot be altered or lowered that may be contraindicated for TMS treatment

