Subjects in the active TMS treatment arm will be tapered off their antidepressant medication as soon as they have signed consent according to the study doctor's direction. Subjects in the TMS active arm will remain antidepressant medication free for the duration of the study. If these subjects deteriorate during course of the study they will be removed from the study and normal clinical care will resume. They will complete a PHQ-9 and QIDS at this time. Their data will be used in the final analysis of study. Deterioration or relapse will be determined by the study doctor clinical judgement.

For subjects in the active TMS treatment arms, a dosing procedure (Motor Threshold) will need to be performed by any person the study PI delegates this authority to, each month immediately before the first treatment of each monthly treatment block. The Motor Threshold (MT) is used to determine the % TMS machine output or dosage, needed to treat. The procedure consists of the TMS certified operator placing the TMS machine treatment coil on the patient's head, corresponding to an area over the patients left Motor Cortex of his/her brain. Then the TMS machine intensity is turned up or down and the coil is moved around on patient's head to determined how much energy is need to elicit a muscle twitch in the right abductor pollicis brevis muscle (APB). Then a computer algorithm helps determine the correct intensity that should be used for the next 5 treatments. An additional computer algorithm uses head measurements of circumference, Nasion to Inion, and Tragus to Tragus, to determine where the TMS treatment coil will be located to treat over the Dorsolateral Prefrontal Cortex (DLPFC). This procedure must be completed each month prior to the monthly treatment block.

If a patient drops out of the study for any reason their data up to that point will be retained and used, this will be discussed with the potential patient during the consent process, and described in the consent itself.

The last treatment visit when a patient completes the treatment portion of the study or has finished their last monthly assessment visit if they are not in an active treatment arm, will be an end study visit (this could be the last treatment/assessment visit if time allows). At this visit the TMS MD will discuss end of study and possible future clinical care that maybe necessary for subject when they switch back over to clinical realm and are no longer part of the study.

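### Section VIII says the risks are unchanged from clinical TMS, but the active arm is also taken off antidepressants; section XII does not bring removals for deterioration together for the pause decision

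*Protocol*

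**What the plan says.** Section VIII of the protocol (Potential Risks/Adverse Events) opens its risk statement with: "The machine and treatment protocols are the same used in the clinical setting, therefore the risks are the same". The risks it goes on to name are headache, pain at the treatment site, dental pain, eye pain, facial twitching and, as the one serious risk, seizure at about 1 in 30,000 treatments.

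Elsewhere the protocol describes a wider intervention for the active arm:

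- Section I states the main purpose as maintaining responders with TMS "while off their antidepressant medication".
- Section V makes the taper an entry condition for one arm: "Must be able to taper off antidepressant medication within 2 months of signing consent of study (treatment group only").
- Section VII says "Subjects in the active TMS treatment arm will be tapered off their antidepressant medication as soon as they have signed consent", under the study doctor's direction, and "Subjects in the TMS active arm will remain antidepressant medication free for the duration of the study".

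On worsening, section VII says "If these subjects deteriorate during course of the study they will be removed from the study and normal clinical care will resume" and "Deterioration or relapse will be determined by the study doctor clinical judgement".

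On oversight, section XII has no DSMB. All adverse events are logged. The study doctor decides whether they lie within what is normal for TMS, using clinical experience and safety data on TMS, and may pause the study if they do not. Local IRB rules decide what is submitted to the IRB.

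**The concern.** The premise in section VIII concerns the machine and the stimulation protocols. The conclusion concerns risk without any limit. That step would be sound only if stimulation were all that the study does to a subject. In the active arm the study also withdraws a drug treatment and keeps it withdrawn. Section VIII is the protocol's only risk section, and it mentions neither the taper nor the medication-free period.

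Two things are at stake. First, the IRB and the study staff read a risk statement that leaves out part of what the study does to one arm. Second, the pause test in section XII is framed around what is normal for TMS. Several active-arm subjects could deteriorate after the taper and each be handled correctly as an individual, without the text asking whether the removals together call for a pause.

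**Working it through.** The protocol states no figure on this point, so there is none to reproduce. The check is a comparison of sections, with some arithmetic for scale.

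**1. What the premise covers.** Section II uses the word for stimulation settings: "This study will use the exact same protocols used in the acute treatment setting, except that treatments will be given monthly not daily". The premise of section VIII therefore speaks to the device and its settings, and says nothing about drug treatment.

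**2. What the active arm receives.** Sections I, V and VII together give stimulation, a taper starting at consent, and a medication-free period lasting for the study. The taper condition is confined to the treatment group and the study doctor directs it. It is therefore a study procedure and not background care. Nothing in the protocol requires the same of the other arm.

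**3. What section VIII lists.**

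| Source of risk | Risks named in section VIII |
|---|---|
| Stimulation | 6 (headache, site pain, dental pain, eye pain, facial twitching, seizure) |
| Antidepressant taper | 0 |
| Medication-free period | 0 |

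**4. How many subjects are affected.** Section VI plans 60 subjects in each arm of 120, so the rule applies to 60/120 = 50%. The share entering on an antidepressant is not stated. Assuming 50% to 100%, the number tapered is 60 × 0.5 = 30 to 60 × 1.0 = 60.

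**5. Scale of the listed and the unlisted kind of event.** Section VII plans 60 treatments per active subject, and section I gives background rates after acute TMS of close to 40% worsening and another 10% relapse within 6 months.

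- Treatments: 60 × 60 = 3,600 if all are given.
- Expected seizures: 3,600/30,000 = 0.12. The chance of at least one is 1 − (1 − 1/30,000)^3,600 = 11.3%.
- Subjects worsening at the background rate: 60 × 0.40 = 24.
- Subjects relapsing at the background rate: 60 × 0.10 = 6.

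The 24 and the 6 are background figures. They are not effects of the taper, and the protocol offers no figure for any excess. They show only that mood worsening is a far more likely event in this arm than the one serious risk named.

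**6. What the pause test would catch.**

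- An adverse event atypical of TMS falls outside the normal range and meets the test as written, whatever caused it.
- Mood worsening is different. The figures in section I make worsening common after TMS, so it can fall within the normal range.
- For that kind of event the text provides individual removal (section VII). No sentence says that removals are counted, or that they enter the pause decision.

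**The case against.** The best defence of section VIII is that its sentence is about the machine and its settings, so the risks it means are those of the machine. On that reading the wording is loose and the rest is omission. The reading is possible, but it does not rescue the section: if section VIII covers only device risks, no section covers the others.

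The objections to the section XII part carry more weight, and most of them stand:

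- The taper is directed by the study doctor, and subjects must have a provider who manages their mental health symptoms (section V).
- The visit schedule has the PHQ-9 and QIDS completed before and after every monthly block, so worsening should be seen early.
- Deteriorating subjects are removed and return to clinical care. The study doctor also decides on continuation for other problems that subjects may have, not only device problems (section VIII).
- The same doctor judges deterioration and holds the pause decision, and nothing prevents that doctor from weighing removals.
- Deterioration is also an outcome of this trial, so whether it is logged as an adverse event is a legitimate choice.

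A reader might infer more than the document supports:

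- *That the study doctor's review is the only study-level safety check.* It is not. Section VIII provides for IRB notice of adverse events and unanticipated problems within 5 days when required, and section XII defers to local IRB rules.
- *That an excess of deterioration would be hidden.* It would not be, because the doctor sees every removal.
- *That there is no benchmark for worsening off drug.* Clinical experience is a stated benchmark, and reference 10 is by its title a 12-month study of medication-free TMS responders.
- *That subjects are not told of the taper's risks.* The consent form is not shown, so this cannot be said.

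**Conclusion.** The risk statement in section VIII is wrong as written for the active arm. The protocol's own design adds a study-directed drug withdrawal and a medication-free period, and the only risk section names neither. This concerns 60 of 120 subjects by rule, and 30 to 60 in practice if 50% to 100% enter on an antidepressant, which is an assumption. It should be corrected.

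The section XII point holds only in a narrow form and carries less weight. Mood worsening within the normal range for TMS is dealt with subject by subject, and no text brings the removals together for the pause decision.

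The conclusion rests on the text of sections I, II, V, VII, VIII and XII. It does not rest on any harm rate for the taper. The protocol gives none, and none is claimed.

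**What to change.** **Section VIII.** Limit the sentence so that it says only that the *device* risks are the same as in clinical use. Then add, for the active arm, the risks of the study-directed drug change: discontinuation effects during and after the taper, and relapse or worsening of depression while off medication.

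**Section XII.** Add one sentence: *removals for deterioration in the active arm are tallied and considered in the study doctor's review when deciding whether to pause.* Leave any threshold to the investigator and the IRB.

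When amending, check that the consent form carries the same risks.

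The cost is a wording amendment, with no added visits, staff or procedures. The downside is a less favourable risk statement and slightly more logging.
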